3 LIST OF ABBREVIATIONS AND DEFINITION OF TERMS

°C	Degree Celsius
ABG	Arterial blood gases
ADA	Anti-Drug Antibody
AE	Adverse event
ANOVA	Analysis of variance
APACHE	Acute Physiology And Chronic Health Evaluation
BMI	Body mass index
CCC	Clinical coordination centre
Cmax	Maximum concentration
CPR	Cardiopulmonary resuscitation
CRF	Case report form
CRO	Contract research organisation
d/D	Day
DBP	Diastolic blood pressure
dl	deciliter
DSMB	Data safety monitoring board
EC	Ethics committee
ECG	Electrocardiogram
eCRF	Electronic case report form
EoI	End of Infusion
EoS	End of Study
GCP	Good clinical practice
h/H	hour
i.v.	intravenous
ICF	Informed consent form
ICH	International council for Harmonisation
ICU	Intensive care unit
IMP	Investigational medicinal product
kg	Kilogram
LC	Liquid chromatography
LR12	Active pharmaceutical ingredient in MOTREM
LPLV	Last patient last visit
MAP	Mean arterial pressure
mg	Milligram
mM	Millimolar
MOTREM	Clinical formulation of LR12
MS	Mass spectrometry
NOAEL	No Observed Adverse Effect Level
P/F	PaO ₂ /FiO ₂ ratio of arterial oxygen partial pressure to fractional inspired oxygen
PD	Pharmacodynamics
Ph.Eur.	Pharmacopoea Europaea
PK	Pharmacokinetics
PW	Premature withdrawal
Q	Quarter (calendar)
QT	QT interval (ECG)
QTc	Corrected QT interval
RNO	Ribonucleic acid
SAE	Serious Adverse Event
SBP	Systolic blood pressure

SNP	Single Nucleotide Polymorphism
SOFA	Sequential Organ Failure Assessment
SOM	Study operations manual
sTLT-1	Soluble TREM Like Transcript 1
sTREM-1	Soluble Triggering Receptor Expressed on Myeloid Cells 1
SUSAR	Suspected unexpected drug reaction
TLT-1	TREM Like Transcript 1
TREM-1	Triggering Receptor Expressed on Myeloid Cells 1
UTI	Urinary tract infection

6 INTRODUCTION

6.1 Sepsis

For many years, the clinical features of sepsis were considered the result of an overly exuberant inflammatory host response. More recently, it has become apparent that infection triggers a much more complex, variable and prolonged host response (1,2). In general, proinflammatory reactions (directed at eliminating invading pathogens) are held responsible for “collateral” tissue damage in severe sepsis, whereas anti-inflammatory responses are implicated in the enhanced susceptibility to secondary infections. Key inflammatory reactions during sepsis include activation of leukocytes, the release of cytokines and chemokines, activation of the coagulation system and activation of endothelial cells (3). Inflammatory reactions are perpetuated in sepsis at least in part due to the release of so-called damage-associated patterns (or alarmins) from injured host cells (4). On the other hand, patients with sepsis demonstrate evidence of immune suppression, which is characterised (amongst other) by a reduced capacity of leukocytes to react to bacteria or bacterial products (5). Sepsis-induced immune suppression is characterised by loss of immune cells due to apoptosis, and held responsible for secondary nosocomial infections and late mortality (2,5).

An international group of experts has recently updated the criteria for the clinical diagnosis of sepsis and septic shock (“Sepsis-3”) (6).

With an incidence of approximately 150 cases of hospital treated severe sepsis per 100,000 inhabitants in the “western” world (USA, Europe, Australia) and mortality rates of almost 30%, severe sepsis is a leading cause of death accounting for up to 5 million deaths worldwide (7). Epidemiological data in Europe confirm this information. The direct costs for the treatment were estimated to approx. EUR 30,000 per sepsis case, with costs higher in the US and lower in Europe. However, indirect costs from the loss of productivity were estimated to account for 70-80% of cost (8).

6.2 Treatment of Sepsis

The Surviving Sepsis Campaign was created in 2002 and covers severe sepsis management guidelines and a sepsis performance improvement program, composed by an international consortium of critical care, infectious disease, and emergency medicine professional societies. The second revision of the guidelines was published in 2013 (9). The most important components of the guidelines are structured in two “bundles” of care: an initial management bundle to be accomplished within 3-6 hours of presentation and a management bundle to be accomplished within 24 hours. Implementation of the bundles is associated with improved outcome (10).

The principles of the initial management bundle are to provide cardiorespiratory resuscitation and diminish the immediate danger of the underlying infection. Resuscitation involves intravenous fluids, vasopressors and mechanical ventilation where needed. The initial management of infection entails identifying the most likely source of infection, obtaining cultures, instigating empiric antimicrobial therapy and pus drainage where appropriate. The choice of empirical antibiotic treatment depends on the site of infection, the location the infection was acquired (e.g. community, nursing home or hospital), medical history, and local microbial susceptibility patterns.

Importantly, unlike other major illnesses, treatment for sepsis is nonspecific and restricted to support of failing organ functions. There are no approved drugs that specifically target sepsis. It is expected that sepsis will remain an important clinical problem in the future, caused by a combination of factors, including the ageing population, aggressive therapies for chronic

diseases (in particular malignancies) and emerging antibiotic resistance. As such, there is an unmet clinical need for effective therapeutic interventions in severe sepsis.

6.3 MOTREM for the Treatment of Septic Shock

The Triggering Receptor Expressed on Myeloid Cells 1 (TREM-1) is an immunomodulatory receptor expressed on innate immune cells (11–14). The biological function of TREM-1 is the amplification of inflammation. In sepsis, this amplification may result in an exuberant and hyperactivated immune state (“genomic storm”) (15), which is responsible for the onset and progression of the disease.

LR12 is a 12 amino-acid peptidic fragment derived from TREM-Like Transcript-1 (TLT-1), a receptor protein belonging to the TREM-1 family. LR12 can bind to (“trap”) TREM-1 ligand and thereby modulating the amplification of the immune response caused by the activation of TREM-1 both in sepsis and myocardial infarction (16,17).

TREM-1-induced activation of several intracellular proteins involved in inflammation as well as cytokine production in human neutrophils and monocytes was shown to be downmodulated by LR12 *in vitro* in a dose dependent manner. In non-activated resting lymphocytes LR12 does not modify several intracellular signalling pathways analysed, including those involved in inflammation.

As sepsis is a life-threatening disease characterised by a hyperactivated immune response, it is of paramount importance to consider the safety of LR12, when administered in a condition in which the immune system is activated. In every preclinical model of sepsis and septic shock studied, the administration of LR12 was associated with protective effects especially on the intensity of inflammation, cardiovascular system and survival:

In animal models of peritonitis (mouse and rat), a mortality of 90 to 95% was observed within 7 days following the onset of sepsis. The administration of LR12 significantly decreased mortality and sepsis related symptoms, even when administered 24 hours after the initial injury. Inflammatory response markers were shown to be reduced, without completely abrogating them. Administration of LR12 also resulted in reduction of sepsis-induced tissue abnormalities and showed protective effects on the cardiovascular system. In addition, the administration of LR12 improved bacterial clearance in mouse model of peritonitis. In a mini-pig model of peritonitis, the administration of LR12 led to a significant decrease of vasopressor (norepinephrine) administration which translates to a substantial protective effect of the cardiovascular system. LR12 also prevented sepsis-induced tissue abnormalities and dysfunctions in this model.

During an experimental monkey endotoxemia model, the administration of LR12 attenuated the endotoxin-induced blood pressure decrease and release of several inflammatory cytokines in blood. In this model the cytokines IL-6, IL-8, TNF- α , CCL2, CCL3 and CCL4 were diminished to intermediate levels but not completely abrogated.

Animal toxicity studies showed that treatment with MOTREM (formulated LR12) was safe and well tolerated up to doses of 140 mg/kg/day.

In a phase I study in healthy volunteers, treatment with MOTREM was found to be safe and well tolerated up to the highest dose tested (6 mg/kg/h for 7h45).

For details please refer to the current Investigator’s Brochure.

MOTREM, therefore, represents a new class of anti-sepsis drug. The rationale for taking this compound into further development is the expectation that it could be an effective new anti-sepsis therapeutic agent and the first causal treatment for sepsis.

The aim of this study in patients with septic shock is to obtain information on the safety, tolerability, pharmacokinetics and preliminary pharmacodynamics and efficacy of MOTREM. Data from this study will help to design subsequent studies in patient populations clinically and therapeutically relevant with this new class of compound.

6.4 Risk-Benefit Evaluation

6.4.1 Potential Benefits

MOTREM (LR12) will be given to patients mainly for research and development purposes. Although a beneficial effect of MOTREM has not yet been confirmed in humans, patients receiving IMP may benefit from its pharmacological action.

Over the long-term, the larger patient population with septic shock may benefit from MOTREM if its development will be successful.

6.4.2 Potential Risks

MOTREM was found to be safe and well tolerated during preclinical safety pharmacology and toxicology testing (NOAEL was defined as 140 mg/kg/day for 14 days). In addition, MOTREM was found to be safe and well tolerated up to the highest dose tested (6 mg/kg/h for 7h45) in a phase I clinical study in healthy volunteers. There was no evidence of immunogenicity of MOTREM nor the appearance of anti-MOTREM antibodies (ADA).

There is currently no clinical experience with MOTREM in patients with septic shock.

As with all protein products, administration of MOTREM may result in immunogenicity. Immunogenicity-related risks include lack of efficacy, hyper-acute or acute reactions, delayed reactions or autoimmunity. LR12 is a peptide derived from a highly conserved human protein; it is expected to have a low immunogenic profile. An exposure to study drug of up to five days is not expected to result in triggering an immune response in the study patients. However, since the possibility of triggering an immune response against it in humans still exists, ADA responses will be monitored and patients will be surveyed for other manifestation of immunogenicity-related reactions.

Because of its mechanism of action, MOTREM may have an impact on the immune system, either on immune cells or on immune responses. Since MOTREM targets activated immune cells in septic shock patients, the treatment with formulated LR12 may interfere with inflammatory/immune responses in an undesired way. However, in preclinical models, treatment with LR12 resulted in a diminution of proinflammatory cytokine expression and concentration and not in a complete abrogation of cytokine responses. In addition, LR12 treatment resulted in a better bacterial clearance in a polymicrobial sepsis murine model. Patients will be carefully monitored with laboratory analysis and changes in immune parameters will be followed. INOTREM is maintaining a risk management plan for the clinical development of MOTREM, which describes potential risks of MOTREM administration, their monitoring and measures for mitigation.

Other risks include infusion site associated reactions.

6.4.3 Benefit-Risk Assessment

The benefit risk ratio of the study design is considered favourable because (i) throughout the study, all patients receive standard therapy for the treatment of their septic shock, (ii) progression to next dose level/next stage only after evaluation of data from previous groups/cohorts and approval from an independent Data Safety Monitoring Board (DSMB) and (iii) patients with a deterioration of their disease will be withdrawn from the study.

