9.5 Withdrawal of Patients

The investigator will withdraw a patient from the study (i.e. from any further study medication or study procedure) for one or more of the following reasons:

- At the request of the patient or legal representative (withdrawal of consent)
- If, in the investigator's opinion, continuation of the study would be detrimental to the patient's well-being
- Use of/need for a prohibited medication which in the opinion of the Sponsor or Investigator may jeopardise the study results or represent a risk to the participant
- Major violation of the protocol
- Is withdrawn from the study upon the request of Sponsor, including if Sponsor terminates the study.

As far as possible, all examinations scheduled for the final study day (EOS) must be performed on all patients who receive the investigational product but do not complete the study according to the protocol. In any case, the respective case report form (CRF) section entitled "End of Study" as well as survival status at days 28 and 90 must be completed.

In all cases, the reason for and date of withdrawal must be recorded in the CRF and in the patient's medical records. The patient must be followed up to establish whether the reason was an AE, and, if so, this must be reported in accordance with the procedures in section 13 on page 42.

The investigator must make every effort to contact patients lost to follow-up. Attempts to contact such patients must be documented in the patient's records (e.g., times and dates of attempted telephone contact, receipt for sending a registered letter). At least two documented attempts to contact the patient must be made before a patient can be considered lost to follow-up.

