10.6.2 Methods for Unblinding a Patient

Individual randomisation code for each randomised patient will be available from electronic Case Report Form (eCRF). The investigator may request unblinding of a patient's treatment assignment mainly in the case of an emergency, when knowledge of the study treatment is essential for the appropriate clinical management or welfare of the patient.

In the event of an emergency, an unblinding tool will be accessible from patient overview in the eCRF and allow to know for each patient his study drug assignment.

Unblinding should only be considered for the safety of the patient. If unblinding is deemed necessary by the investigator, the investigator or designee can unblind the patient's treatment allocation using a specific function in eCRF. The investigator or designee must note the date, time and reason for unblinding and inform the sponsor of unblinding as soon as practicably possible.

The patient whose treatment has been unblinded will continue in the study.

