11.3.2 Treatment Period (Day 1 to Day 4)

During the treatment period of up to 5 days, the following assessments will be performed daily (approximately at the same time of day):

- Concomitant therapy
- SOFA score
- Vital signs
- ECG
- Vasopressor use
- Invasive mechanical ventilation
- Intubation
- Mortality
- Adverse events
- Blood sample for ABG and P/F
- Blood samples for laboratory tests (according to schedule provided in Table 2):
 - Clinical Laboratory
 - Pharmacokinetics
 - Biomarkers
 - RNA profile
 - Plasma samples for retention (Day 1 only)
- Continued treatment with MOTREM i.v. (according to Table 5 or Table 6)

11.3.3 End of Infusion/Day 5

Patients will be treated until 12 (± 2) hours after the resolution of their septic shock (defined as vasopressor withdrawal) with a maximum treatment of 5 days (120 (± 2) hours). An

interruption of vasopressor treatment of up to 6 hours is permitted and not considered vasopressor withdrawal).

Patients may also be withdrawn from treatment for other reasons (see section 9.5).

At the end of treatment, the i.v. infusion will be stopped and the following assessments will be performed:

- Concomitant therapy
- SOFA score
- Vital signs
- Weight
- ECG
- Vasopressor use
- Invasive mechanical ventilation
- Intubation
- Mortality
- Adverse events
- Blood sample for ABG and P/F
- Blood samples for laboratory tests (according to schedule provided in Table 2):
 - Clinical Laboratory
 - pharmacokinetics
 - biomarkers
 - RNA profile

If the treatment is stopped any day before D5, the assessments listed above will be performed only once the day of the end of infusion.

For all patients alive, the SOFA score will however be calculated until day 5, no matter when the study treatment stopped. This data will be collected to the extent available in source data and analysed post-hoc (see section 15.5).

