13.2.2 Other Events to be Treated as Serious Adverse Events

Exposure to drug during pregnancy: In principle, pregnancy and the lactation period are exclusion criteria for clinical studies involving investigational drugs, which are not directly related to the respective conditions. In the event of a pregnancy occurring during the course of this particular study, the patient should be withdrawn from study, but closely followed-up during the entire course of the pregnancy and postpartum period.

Investigational Product Complaints: Pharmaceutical technical complaints associated with the investigational product must be reported immediately. The same reporting timelines as for SAEs apply.

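### Withdrawal for deterioration ends study procedures as well as drug, so the Day 10 antibody sample is not required; separately, daily safety assessments stop at end of infusion in all patients

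*Combined protocol and SAP*

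**What the plan says.** Section 6.4.3 gives three grounds for a favourable benefit-risk ratio. The third is that "patients with a deterioration of their disease will be withdrawn from the study". Deterioration is not defined there.

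Section 9.5 lists the reasons for withdrawal and explains the term: "i.e. from any further study medication or study procedure". Deterioration is not on the list. The nearest entry is the investigator's opinion that "continuation of the study would be detrimental to" the patient. Section 11.3.3 sends stops of treatment to the same list: "Patients may also be withdrawn from treatment for other reasons (see section 9.5").

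For treated patients who do not complete, section 9.5 adds safeguards: "As far as possible, all examinations scheduled for the final study day (EOS) must be performed". Survival at Days 28 and 90 must also be completed, and "In all cases, the reason for and date of withdrawal must be recorded in the CRF".

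In two places the protocol says what continues. On unblinding: "The patient whose treatment has been unblinded will continue in the study". On pregnancy: "the patient should be withdrawn from study, but closely followed-up".

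For every patient whose infusion ends before Day 5, section 11.3.3 has the listed assessments done once, on the day the infusion ends. SOFA alone continues to Day 5. Section 15.5 retrieves it from source records, because the gaps had been treated as missing in an analysis already done.

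**The concern.** Safety is the primary endpoint (section 15.1.3). It includes anti-LR12 antibodies, laboratory tests, ECG, vital signs and AEs. Sections 6.4.3, 9.5 and 11.3.3 read together create no general status of off drug but still on study. A patient stopped for worsening could therefore leave scheduled procedures within the first five days. That loss would be informative, because it would fall on the sickest patients in the first study of this drug in septic shock (section 8.5.1). Section 15.1.1 leaves missing data missing.

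The Day 1-5 issue is separate and affects more patients. Infusion length is set mainly by when vasopressors are withdrawn, which happens after randomisation and which the drug is meant to influence. From the first early stop onward, each daily summary of laboratory values, vital signs and ECG is restricted to patients still on infusion. If shock resolves at different speeds in different arms, the arms are no longer comparable at those visits.

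**Working it through.** **Step 1. What remains after a withdrawal for worsening.**

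| Item | Where | Status |
|---|---|---|
| Day 10 ADA (and Coombs, French sites) | 11.3.6, 12.13.1, Table 2 | Separate visit, not an end-of-study examination; no text keeps it |
| Day 28 examinations, including ADA and AEs | 9.5, 11.3.4 | Kept, as far as possible |
| New AEs to Day 28 | 13.1 and 13.4 against 9.5 | Section 13 makes no exception for withdrawn patients; 9.5 ends procedures; neither says which governs |
| Sepsis-related clinical events | 12.9 | No collection period stated |
| AEs with fatal outcome | 13.2.1 | Reported even when death follows the end of treatment |
| AEs already open | 13.3 | Followed up |
| Survival, Days 28 and 90 | 9.5 | Required |
| SOFA to Day 5 | 11.3.3, 15.5 | From source data where available |

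The clear gap is the Day 10 sample. Table 2 has only two ADA samples after baseline, Day 10 and Day 28. When Day 10 is missed, everything rests on Day 28.

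**Step 2. Size for ADA (illustrative).** The plan's figure reproduces: stage 1 has 3 × (3 + 1) = 12 patients, stage 2 has 4 × 9 = 36, total 48. Each dose level has 3 + 9 = 12 (section 15.2), and placebo also has 3 + 9 = 12.

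With no positive patient among n sampled, the one-sided 95% upper limit is 1 − 0.05^(1/n):

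| n | 12 | 11 | 10 | 9 | 8 |
|---|---|---|---|---|---|
| Upper limit | 22.1% | 23.8% | 25.9% | 28.3% | 31.2% |

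*Upper bound.* If 1 to 4 of 12 patients gave neither post-baseline sample, the limit would rise from 22.1% to between 23.8% and 31.2%.

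*Deaths separated.* Patients who die before Day 10 are lost under any wording. Provided Day 28 samples are obtained from survivors, the rule costs only those withdrawn for worsening who die between Day 10 and Day 28. Let d be early deaths and k such patients, so n falls from 12 − d to 12 − d − k. Deaths are capped at 4 of 12, an assumption loosely based on the almost 30% mortality that section 6.1 gives for severe sepsis.

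| d | k | Limit without the rule | Limit with the rule | Difference (points) |
|---|---|---|---|---|
| 0 | 1 | 22.1% | 23.8% | 1.7 |
| 0 | 2 | 22.1% | 25.9% | 3.8 |
| 2 | 1 | 25.9% | 28.3% | 2.4 |
| 2 | 2 | 25.9% | 31.2% | 5.3 |
| 3 | 1 | 28.3% | 31.2% | 2.9 |

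With k = 0 the difference is zero.

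**Step 3. Size for Day 1-5 summaries (illustrative).** Suppose infusion ended before Day 5 in 25%, 50% or 75% of 12 patients. Then 9, 6 or 3 contribute at Day 5. With the same SD and ignoring deaths, the standard error grows by √(12/n): √(12/9) = 1.15, √(12/6) = 1.41, √(12/3) = 2.00. This measures lost precision only. The selection of patients still in shock comes on top, and the documents give nothing from which to size it.

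**The case against.** A reader might infer that AE collection simply stops when a deteriorating patient is withdrawn. The documents do not support that. Sections 13.1 and 13.4 run AE recording from consent to Day 28 without exception. Section 11.3.4, whose heading covers premature withdrawal, lists AEs and SAEs. Section 13.2.1 covers fatal AEs after the end of treatment. The pregnancy rule shows that withdrawal need not bar follow-up. What stands is a wording conflict between 9.5 and 13.4, with the weight on the side of continued recording.

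A reader might also infer that the cause of such withdrawals would be hidden. Worsening shock does go to separate sepsis-event pages (section 13.1), so the summary of AEs leading to discontinuation may miss it. But section 15.1.5 describes sepsis events by arm and visit, and the withdrawal reason is in the CRF. Section 15.1.4 does not name withdrawal reasons, but the protocol leaves analysis detail to a separate SAP.

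Three further objections have force. Section 6.4.3 is rationale, while 9.5 is the operative list and needs an investigator's judgement, so the path may be used rarely. Section 6.4.2 does not expect an immune response to five days of exposure. With a half-life of about 2 minutes (section 9.6), tying daily checks to the infusion is defensible, and section 13.3 makes clinically relevant deteriorations AEs. These reduce the likely size. They do not supply the missing Day 10 rule, and AE reports do not replace daily values in a by-visit summary.

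**Conclusion.** The point holds in limited form. The Day 10 ADA sample is not required after a withdrawal for worsening, nor is the Coombs test at French sites. The Day 28 examinations are protected only as far as possible, and the text leaves AE recording after withdrawal ambiguous rather than ended. Separately, daily laboratory, vital-sign and ECG data end with the infusion for everyone, and only SOFA is repaired.

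The size is unknown: the documents give no withdrawal rate, timing of deaths or infusion durations. For ADA the effect may be zero if Day 28 samples are obtained. The 1.7 to 5.3 points arise only if at least one patient per arm is withdrawn for worsening and then dies between Day 10 and Day 28. The larger figure needs all four assumed deaths, two early and two later, with both later ones withdrawn for worsening. The Day 1-5 limb depends on no withdrawals at all and is the more certain of the two. This should be corrected; it does not invalidate the study.

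**What to change.** **Wording.** Change 6.4.3 and 9.5 so that deterioration stops study drug only. Day 10 samples, AE and sepsis-event collection to Day 28, Day 28 assessments and Day 90 survival then continue unless consent is withdrawn. State in 13.4 that AE recording to Day 28 applies after drug stop. In 11.3.3, record routine laboratory and vital-sign values to Day 5 whenever the infusion stops.

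**What can still be done.** This version follows an analysis already run, so rewording may no longer change how any patient is handled. Two steps remain useful:

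- Extend the section 15.5 source-data retrieval to routine laboratory and vital-sign values to Day 5.
- Tabulate by arm the withdrawals whose recorded reason was deterioration.

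Do not re-collect AEs retrospectively. Section 15.4 allows sponsor and investigators to be unblinded after the last Day 28 visit, so ascertainment and causality ratings could be biased.

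**Cost.** A little more data entry and one extra table. Laboratory values come from routine samples (Table 2), and section 9.5 already requires the withdrawal reason. Missed Day 10 ADA samples cannot be recovered.
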